### 5.1 Consent Process:

Check all applicable boxes below:

**Informed consent will be sought and documented with a written consent form [Complete Sections 5.2 and 5.6]**

**Implied or verbal consent will be obtained – subjects will not sign a consent form (waiver of written documentation of consent) [Complete Sections 5.2, 5.3 and 5.6]**

**Informed consent will be sought but some of the elements of informed consent will be omitted or altered (e.g., deception). [Complete section 5.2, 5.4 and 5.6]**

**Informed consent will not be obtained – request to completely waive the informed consent requirement. [Complete Section 5.5]**

The following checkbox is for all locations EXCEPT Penn State Health and College of Medicine:

**Exempt Research at all Locations Except Penn State Health and the College of Medicine:** If you believe that the research activities outlined meet one or more of the criteria outlined in "HRP-312-

**Worksheet- Exemption Determination.” Please verify by checking this box that if conducting an exempt research study, the consent process will disclose the following (all of which are included in “HRP-590- Consent Guidance for Exempt Research”):**

Penn State affiliation; name and contact information for the researcher and advisor (if the researcher is a student); the activities involve research; the procedures to be performed; participation is voluntary; that there are adequate provisions to maintain the privacy interests of subjects and the confidentiality of the data; and subjects may choose not to answer specific questions.

**If the research includes the use of student educational records include the following language in this section (otherwise delete):** The parent or eligible student will provide a signed and dated written consent that discloses: the records that may be disclosed; the purpose of the disclosure; the party or class of parties to whom the disclosure may be made; if a parent or adult student requests, the school will provide him or her with a copy of the records disclosed; if the parent of a student who is not an adult so requests, the school will provide the student with a copy of the records disclosed.

**Note: If this box has been checked, skip the remainder of section 5 and proceed to section 6 of this protocol. If the investigator’s assessment is inaccurate, an IRB Analyst will request revision to the protocol and that an informed consent form be submitted for review and approval. Except for exemptions where Limited IRB Review (see “HRP-312- Worksheet- Exemption Determination”) is required or where otherwise requested by the IRB, informed consent forms for research activities determined to be exempt without Limited IRB Review are generally not required to be submitted for review and approval by the University Park IRB.**

## 5.2 Obtaining Informed Consent

### 5.2.1 Timing and Location of Consent

Describe where and when the consent process will take place.

Informed consent will be obtained in one of two places. If a potential subject is seen by one of the sub investigators during a clinicians’ office visit, the subject will be consented at that time. Alternatively, potential subjects will be consented in the CVIR suite at Hershey Medical Center where TACE is performed.

### 5.2.2 Coercion or Undue Influence during Consent

Describe the steps that will be taken to minimize the possibility of coercion or undue influence in the consent process.

Subjects will be informed that participation is voluntary and that their decision will not affect their care. A physician study team member will discuss the study with the patients, review the consent, and answer all questions. Subjects can opt out prior to receiving their CEUS.

## 5.3 Waiver of Written Documentation of Consent

Review “HRP – 411 – Checklist – Waiver of Written Documentation of Consent.”

### 5.3.1 Indicate which of the following conditions applies to this research:

The research presents no more than minimal risk of harm to subjects and involves no procedures for which written consent is normally required outside of the research context.

OR

The only record linking the subject and the research would be the consent document and the principal risk would be potential harm resulting from a breach of confidentiality. Each subject

will be asked whether the subject wants documentation linking the subject with the research, and the subject's wishes will govern. (Note: This condition is not applicable for FDA-regulated research. If this category is chosen, include copies of a consent form and /or parental permission form for participants who want written documentation linking them to the research.)

OR

If the subjects or legally authorized representatives are members of a distinct cultural group or community in which signing forms is not the norm, that the research presents no more than minimal risk of harm to subjects and provided there is an appropriate alternative mechanism for documenting that informed consent was obtained. (Note: This condition is not applicable for FDA-regulated research.)

Describe the alternative mechanism for documenting that informed consent was obtained:

Not applicable

**5.3.② Indicate what materials, if any, will be used to inform potential subjects about the research (e.g., a letter accompanying a questionnaire, verbal script, implied consent form, or summary explanation of the research)**

**5.4 Informed consent will be sought but some of the elements of informed consent will be omitted or altered (e.g., deception).**

Review "HRP-410-Checklist -Waiver or Alteration of Consent Process" to ensure that you have provided sufficient information.

**5.4.① Indicate the elements of informed consent to be omitted or altered**

Not applicable

**5.4.② Indicate why the research could not practicably be carried out without the omission or alteration of consent elements**

Not applicable

**5.4.③ Describe why the research involves no more than minimal risk to subjects.**

Not applicable

**5.4.④ Describe why the alteration/omission will not adversely affect the rights and welfare of subjects.**

Not applicable

**5.4.⑤ If the research involves using identifiable private information or identifiable biospecimens, describe why the research could not be practicably be carried out without using such information or biospecimens in an identifiable format.**

Not applicable

**5.4.⑥ Debriefing**

Explain whether and how subjects will be debriefed after participation in the study. If subjects will not be debriefed, provide a justification for not doing so. Add any debriefing materials to the study in CATS IRB.

Not applicable

**5.5 Informed consent will not be obtained – request to completely waive the informed consent requirement**

Review “HRP-410-Checklist -Waiver or Alteration of Consent Process” to ensure that you have provided sufficient information.

**5.5.① Indicate why the research could not practicably be carried out without the waiver of consent**

Not applicable

**5.5.② Describe why the research involves no more than minimal risk to subjects.**

Not applicable

**5.5.③ Describe why the alteration/omission will not adversely affect the rights and welfare of subjects.**

Not applicable

**5.5.④ If the research involves using identifiable private information or identifiable biospecimens, describe why the research could not be practicably be carried out without using such information or biospecimens in an identifiable format.**

Not applicable

**5.5.⑤ Additional pertinent information after participation**

Explain if subjects will be provided with additional pertinent information after participation. If not applicable, indicate “not applicable.”

Not applicable

**5.6 Consent – Other Considerations**

**5.6.① Non-English-Speaking Subjects**

Indicate what language(s) other than English are understood by prospective subjects or representatives.

If subjects who do not speak English will be enrolled, describe the process to ensure that the oral and written information provided to those subjects will be in that language. Indicate the language that will be used by those obtaining consent.

Indicate whether the consent process will be documented in writing with the long form of the consent documentation or with the short form of the consent documentation. Review “HRP-091 –SOP- Written Documentation of Consent” and “HRP-103 -Investigator Manual” to ensure that you have provided sufficient information.

Not applicable

**5.6.② Cognitively Impaired Adults**

Refer “HRP-417 -CHECKLIST- Cognitively Impaired Adults” for information about research involving cognitively impaired adults as subjects.

**5.6.2.1 Capability of Providing Consent**

Describe the process to determine whether an individual is capable of consent.

Not applicable.

#### 5.6.2.2 Adults Unable to Consent

Describe whether and how informed consent will be obtained from the legally authorized representative. Describe who will be allowed to provide informed consent. Describe the process used to determine these individual's authority to consent to research.

For research conducted in the state of Pennsylvania, review "HRP-013 -SOP- Legally Authorized Representatives, Children and Guardians" to be aware of which individuals in the state of Pennsylvania meet the definition of "legally authorized representative."

For research conducted outside of the state of Pennsylvania, provide information that describes which individuals are authorized under applicable law to consent on behalf of a prospective subject to their participation in the procedure(s) involved in this research. One method of obtaining this information is to have a legal counsel or authority review your protocol along with the definition of "children" in "HRP-013 -SOP- Legally Authorized Representatives, Children, and Guardians."

Not applicable.

#### 5.6.2.3 Assent of Adults Unable to Consent

Describe the process for assent of the subjects. Indicate whether assent will be required of all, some or none of the subjects. If some, indicate which subjects will be required to assent and which will not.

If assent will not be obtained from some or all subjects, provide an explanation of why not.

Describe whether assent of the subjects will be documented and the process to document assent. The IRB allows the person obtaining assent to document assent on the consent document and does not routinely require assent documents and does not routinely require subjects to sign assent documents.

Not applicable.

### 5.6.3 Subjects who are not yet adults (infants, children, teenagers)

#### 5.6.3.1 Parental Permission

Describe whether and how parental permission will be obtained. If permission will be obtained from individuals other than parents, describe who will be allowed to provide permission. Describe the process used to determine these individual's authority to consent to each child's general medical care.

For research conducted in the state of Pennsylvania, review "HRP-013-SOP- Legally Authorized Representatives, Children and Guardians" to be aware of which individuals in the state of Pennsylvania meet the definition of "children."

For research conducted outside of the state of Pennsylvania, provide information that describes which persons have not attained the legal age for consent to treatments or procedures involved in the research, under the applicable law of the jurisdiction in which research will be conducted. One method of obtaining this information is to have a legal counsel or authority review your protocol along with

the definition of "children" in "HRP-013-SOP- Legally Authorized Representatives, Children, and Guardians."

Not applicable

#### 5.6.3.2 Assent of subjects who are not yet adults

Indicate whether assent will be obtained from all, some, or none of the children. If assent will be obtained from some children, indicate which children will be required to assent. When assent of children is obtained describe whether and how it will be documented.

Not applicable

### 6.0 HIPAA Research Authorization and/or Waiver or Alteration of Authorization

This section is about the access, use or disclosure of Protected Health Information (PHI). PHI is individually identifiable health information (i.e., health information containing one or more 18 identifiers) that is transmitted or maintained in any form or medium by a Covered Entity or its Business Associate. A Covered Entity is a health plan, a health care clearinghouse or health care provider who transmits health information in electronic form. See "HRP-103 -Investigator Manual" for a list of the 18 identifiers.

If requesting a waiver/alteration of HIPAA authorization, complete sections 6.2 and 6.3 in addition to section 6.1. The Privacy Rule permits waivers (or alterations) of authorization if the research meets certain conditions. Include only information that will be accessed with the waiver/alteration.

#### 6.1 Authorization and/or Waiver or Alteration of Authorization for the Uses and Disclosures of PHI

Check all that apply:

- Not applicable, no identifiable protected health information (PHI) is accessed, used or disclosed in this study. [Mark all parts of sections 6.2 and 6.3 as not applicable]**
- Authorization will be obtained and documented as part of the consent process. [If this is the only box checked, mark sections 6.2 and 6.3 as not applicable]**
- Partial waiver is requested for recruitment purposes only (Check this box if patients' medical records will be accessed to determine eligibility before consent/authorization has been obtained). [Complete all parts of sections 6.2 and 6.3]**
- Full waiver is requested for entire research study (e.g., medical record review studies). [Complete all parts of sections 6.2 and 6.3]**
- Alteration is requested to waive requirement for written documentation of authorization (verbal authorization will be obtained). [Complete all parts of sections 6.2 and 6.3]**

#### 6.2 Waiver or Alteration of Authorization for the Uses and Disclosures of PHI

##### 6.2.1 Access, use or disclosure of PHI representing no more than a minimal risk to the privacy of the individual

###### 6.2.1.1 Plan to protect PHI from improper use or disclosure

Include the following statement as written – DO NOT ALTER OR DELETE unless this section is not applicable because the research does not involve a waiver of authorization. **If the section is not applicable, remove the statement and indicate as not applicable.**

Not applicable

**6.2.1.2**

**Plan to destroy identifiers or a justification for retaining identifiers**

Describe the plan to destroy the identifiers at the earliest opportunity consistent with the conduct of the research. Include when and how identifiers will be destroyed. If identifiers will be retained, provide the legal, health or research justification for retaining the identifiers.

Not applicable

**6.2.2 Explanation for why the research could not practically be conducted without access to and use of PHI**

Provide an explanation for why the research could not practically be conducted without access to and use of PHI.

Not applicable

**6.2.3 Explanation for why the research could not practically be conducted without the waiver or alteration of authorization**

Provide an explanation for why the research could not practically be conducted without the waiver or alteration of authorization.

Not applicable

**6.3 Waiver or alteration of authorization statements of agreement**

By submitting this study for review with a waiver of authorization, you agree to the following statement – DO NOT ALTER OR DELETE unless this section is not applicable because the research does not involve a waiver or alteration of authorization. **If the section is not applicable, remove the statement and indicate as not applicable.**

Not applicable

**7.0 Study Design and Procedures**

Data collection materials that will be seen or used by subjects in your study must be uploaded to CATS IRB (<http://irb.psu.edu>). **DO NOT** include any actual data collection materials in this protocol (e.g., actual survey or interview questions)

**7.1 Study Design**

Describe and explain the study design.

This is a prospective trial to determine if contrast enhanced ultrasound (CEUS) is non-inferior to CT or MRI in patients with hepatocellular carcinoma (HCC) following transcatheter arterial chemoembolization (TACE) treatments. All patients will receive standard of care CT/MRI and will also get a contrast ultrasound to directly compare.

Timepoint 0: You agree to take part in the study at the time of your first TACE treatment.

Timepoint 1:  
• CT or MRI and CEUS  
• Complete short survey

Timepoint 2: Return for follow-up standard of care imaging (either a CT or MRI).

## 7.2 Study Procedures

Provide a step by step description of all research procedures being conducted (broken down by visit, if applicable) including such information as below (where and when applicable); describe the following:

- HOW: (e.g., data collection via interviews, focus groups, forms such as surveys and questionnaires, medical/school records, audio/video/digital recordings, photographs, EKG procedures, MRI, mobile devices such as electronic tablets/cell phones, observations, collection of specimens, experimental drug/device testing, manipulation of behavior/use of deception, computer games, etc.)
- WHERE: (e.g., classrooms, labs, internet/online, places of business, medical settings, public spaces, etc.)

Subject demographics, disease state, and tumor characteristics, CT/MRI and CEUS results will be recorded and entered in REDCAP and Oncore.

### 7.2.1 Timepoint 0

Provide a description of what procedures will be performed on visit 1 or day 1 or pre-test in order of how these will be done. If your study only involves one session or visit, use this section only and indicate 7.2.2 as not applicable.

Our proposed study population includes subjects with diagnosed HCC, who are treated with TACE. Patients will be identified and enrolled at the time of initial TACE.

### 7.2.2 Timepoint 1

Provide a description of what procedures will be performed on visit 2 or day 2 or post-test in order of how these will be done. If your study involves more than two sessions or visits replicate this section for each additional session or visit (e.g., 7.2.3, 7.2.4, etc.).

Following initial TACE, patients will receive a CT or MRI, as routinely ordered in the post-TACE setting, to assess for residual or new HCC. The timing of this follow-up occurrence will be followed as routinely ordered by the patients' providers and not be decided upon or affected by involvement in the trial. At this same imaging follow-up visit, patients will also receive a one-time additional contrast-enhanced ultrasound (CEUS). This visit will be performed at either the main hospital or our East Campus, depending on availability and patient needs. MRI, CT, and CEUS will be completed at the same location (i.e., both CT/MRI & CEUS will be completed at either the main hospital or East campus), allowing patient convenience and privacy to simply move between rooms for both exams.

The CEUS will be performed and interpreted by a single radiologist, who is blinded to the CT/MRI, but not to the original tumor site and any prior images. A similarly blinded second radiologist will provide a second read of the CEUS to ensure accuracy at a later date. The same radiologists will be responsible for performing each task for research purposes and will both be members of the research study team. Results from the CEUS will not generate a formal report in the electronic medical record, but will be used only for the research study and entered into REDCAP. The CT or MRI will be interpreted formally by a clinical radiologist, and be dictated and entered into the electronic medical record as standard of practice, outside of the scope of this study. The patient will be administered a short survey about the modalities at the conclusion of their exams utilizing grading on a Likert scale.

### 7.2.3 Timepoint 2

Per standard clinical care, patients typically return for repeat imaging (CT/MRI) within 2-4 months following the first imaging visit. The decision for follow-up timing is not part of the study, but is decided upon by their clinical physicians. The results of these studies will be included in our data analysis, but no additional intervention will occur at this time.

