## 1.0 Objectives

### 1.1 Study Objectives

Describe the purpose, specific aims or objectives. State the hypotheses to be tested.

In this study, we propose a prospective trial to determine if contrast enhanced ultrasound (CEUS) is non-inferior to CT or MRI in patients with hepatocellular carcinoma (HCC) following transcatheter arterial chemoembolization (TACE) treatments, in a U.S. population, using Lumason contrast agent. This would be the largest trial to date examining this patient population in the U.S.

The primary objective of our study is to estimate the sensitivity and specificity of the CEUS (Research Timepoint 1) and evaluate for non-inferiority between CEUS and the clinical gold standard of CT/MRI using the Liver Reporting & Data System (LIRAD). We will be assessing the presence of treated or residual tumor, new sites of disease, and portal vein thrombus. Patient factors, such as BMI, underlying liver disease type, alpha fetoprotein level, and size of liver will be recorded. If findings of metastatic disease external to the liver are identified on CT or MRI and not seen on CEUS, they will be recorded.

CEUS, like regular ultrasound, only images specific organs and cannot identify necessarily metastatic disease, as ultrasound cannot image bones and lungs for this purpose.

The second objective of the project will compare the CEUS with a second, standard of care, follow-up CT or MRI (performed 2-4 months later [Research Timepoint 2]). CT can have false negatives due to ethiodol obscuring subtle, early disease and it is possible that CEUS could identify residual disease earlier compared to the gold standards, but would be characterized as a false positive if compared only to the initial imaging (Timepoint 1). This follow-up will evaluate for false positives or negatives on any of the modalities.

The third objective of the project will evaluate patient subjective data in regards to imaging modality preference and possible effects on compliance. The survey will be administered at the conclusion of Timepoint 1 and will include questions about anxiety, comfort, compliance, and modality preference, graded on a Likert scale.

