### 8.3 Statistical methods

Describe the statistical methods (or non-statistical methods of analysis) that will be employed.

Patient demographics and major clinical information described above will be summarized using descriptive statistics. The main outcome variables in primary objective are the incidence of residual tumor and new tumor, which are both binary. The rate of residual/new tumors using CEUS and CT/MRI will be compared using McNemar's test, which is suitable for comparing paired binary variables. The point estimate and 95% confidence interval (CI) of the incidence rate for CEUS and CT/MRI will be reported separately. Due to the limited sample size of this pilot study, the non-inferiority between CEUS vs CT/MRI will be evaluated just by comparing the CIs of the incidence rate for each method, not by a formal statistical non-inferiority test which requires a much larger sample size. A few additional subgroup analyses will be performed to see if the incidence rate varies by stratification (such as BMI group, liver disease type). Due to the exploratory nature of this study no multiple regression models will be used, and no adjustment of the alpha rate will be made due to multiple testing. Treating the CT/MRI as the clinical gold standard, the sensitivity and specificity of CEUS will be estimated with their 95% CIs. The data from secondary objective will be analyzed similarly as those for the primary objective. For tertiary objective, the subjective ratings from patients between the CT/MRI and ultrasound will be compared using nonparametric Wilcoxon Signed-rank tests. The ratings may be further correlated with some of the baseline demographic and clinical factors using nonparametric Kruskal-Wallis tests. All analyses will be performed using statistical software SAS version 9.4 or higher (SAS Institute, Cary, NC, USA). All tests are two-sided and the significance level to be used is 0.05.

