## 13.0 Subject Payment and/or Travel Reimbursements

Describe the amount, type (cash, check, gift card, other) and timing of any subject payment or travel reimbursement. If there is **no** subject payment or travel reimbursement, indicate as not applicable.

Extra or Course Credit: Describe the amount of credit **and** the available alternatives. Alternatives should be equal in time and effort to the amount of course or extra credit offered. It is not acceptable to indicate that the amount of credit is to be determined or at the discretion of the instructor of the course.

Approved Subject Pool: Indicate which approved subject pool will be used; include in response below that course credit will be given and alternatives will be offered as per the approved subject pool procedures.

Subjects will receive a gift card at the conclusion of the CEUS appointment – specifically, after the CEUS AND CT/MRI AND after they have completed the one time survey. Amount is \$50 per subject and is administered one time, at that visit.

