## 15.0 Resources Available

### 15.1 Facilities and locations

Identify and describe the facilities, sites and locations where recruitment and study procedures will be performed.

If research will be conducted outside the United States, describe site-specific regulations or customs affecting the research, and describe the process for obtaining local ethical review. Also, describe the principal investigator's experience conducting research at these locations and familiarity with local culture.

Subjects will be identified and enrolled during the clinician office visit, if seen by a sub investigator or at the time of TACE in the CVIR suite.

Their follow-up CT/MRI and CEUS will be performed at either the main hospital or the East Campus location on the Penn State Health Hershey main campus grounds, due to convenience and privacy of the patient – CT/MRI and Ultrasound will be completed at the same location (in adjacent rooms/same hallway). Patient will not be required to leave the area to have all of the tests done.

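### The order of CT/MRI and CEUS at Timepoint 1 is not set, balanced or recorded, so the paired comparison of patient ratings may credit an order effect to the modality

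*Combined protocol and SAP*

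**What the plan says.** Section 7.2.2 (Timepoint 1) adds the research ultrasound to the routine follow-up: "At this same imaging follow-up visit, patients will also receive a one-time additional contrast-enhanced ultrasound (CEUS"). Both exams take place at one location. The survey comes after both: "The patient will be administered a short survey about the modalities at the conclusion of their exams utilizing grading on a Likert scale". Section 13.0 confirms a single administration, with the gift card given "after they have completed the one time survey". Under Section 1.1 the survey "will include questions about anxiety, comfort, compliance, and modality preference, graded on a Likert scale".

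For the analysis, Section 8.3 says that "the subjective ratings from patients between the CT/MRI and ultrasound will be compared using nonparametric Wilcoxon Signed-rank tests". The only further factors it relates to the ratings are baseline demographic and clinical ones, and it rules out multiple regression. Tests are two-sided at 0.05.

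No section says which exam is done first. Section 7.1 lists the two exams on one line without a sequence. The template prompt in 7.2.2 asks for procedures in the order in which they will be done, but the answer gives none for the two exams. Section 7.4.3 says only that every subject receives CEUS.

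**The concern.** For the survey objective this is a two-condition within-patient comparison, with both conditions experienced close together and rated once at the end. Pairing removes differences between patients. It does not remove a difference between the first and second exam of a double visit, such as fatigue, relief, anxiety carried over from the first exam, or better recall of the most recent one. If one modality comes second more often, the signed-rank test counts that difference as a modality difference.

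A larger sample would not cure this, because the bias depends on the split of orders and not on the number of patients. If the order is not recorded, the effect cannot be examined afterwards either. Section 8.2 says the pilot is meant to test the design and supply data for larger grant applications, so a preference result of this kind would be carried forward.

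**Working it through.** **The plan's own figure.** The plan enrols 34 (Sections 8.1 and 8.2). That number comes from availability and feasibility, with no formula behind it, and no effect size, SD or power is given for the survey. There is nothing to reproduce.

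**Inputs.** From the documents: n = 34 and two-sided alpha 0.05. Assumed: all 34 give complete paired ratings; the paired difference (CEUS minus CT/MRI) has SD 1 within each order group; the true modality difference is 0; and the exam done second is rated d points differently whichever modality it is. The documents give no value for d, so a range is shown.

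**Bias.** A patient's paired difference moves by +d if CEUS is second and by −d if CEUS is first. The mean shift is

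d × (number with CEUS second − number with CEUS first) / 34.

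- Same order for all: d × 34/34 = d.
- 26/8 split: d × 18/34 = 0.53d.
- 17/17 split: 0.

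**Spread.** Mixed orders also widen the paired differences. At 26/8 the variance is 1 + d² × (1 − (18/34)²). With d = 0.5 that is 1 + 0.25 × 0.720 = 1.18, so the SD is 1.086. Holding the SD at 1 would overstate the false-positive rate (32% instead of 28%).

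**False-positive rate** (noncentral t with 33 degrees of freedom, as an approximation to the signed-rank test; noncentrality = shift/SD × √34):

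| Order | d | Shift | SD | Noncentrality | Rate of p < 0.05 |
|---|---|---|---|---|---|
| Same for all | 0.1 | 0.10 | 1 | 0.58 | about 9% |
| Same for all | 0.25 | 0.25 | 1 | 1.46 | about 29% |
| Same for all | 0.5 | 0.50 | 1 | 2.92 | about 81% |
| 26/8 | 0.25 | 0.13 | 1.022 | 0.75 | about 11% |
| 26/8 | 0.5 | 0.26 | 1.086 | 1.42 | about 28% |

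Simulating the signed-rank test itself with the same order for all, and with differences rounded to whole Likert points, gave 27% at d = 0.25 and 77% at d = 0.5. With a 17/17 split the simulated rate was between 3% and 5%, so there was no inflation.

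**Order-averaged estimate.** Take the mean difference within each order group and average the two means. The +d and −d cancel whatever the split. Simulated at 26/8, a test on this estimate rejected in about 5% of runs for d = 0.1, 0.25 and 0.5. The price is precision: the standard error is ½ × √(1/26 + 1/8) = 0.202, against 1/√34 = 0.171 with balanced order, or about 18% wider. If all patients follow one order, the second group is empty and the estimate does not exist.

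**The case against.** **The documents do not show an unbalanced order.** This stands. Two campuses, two reference modalities and a single radiologist performing every CEUS could produce a mixed order. A habitual sequence is plausible because CT/MRI is the booked clinical exam and CEUS the addition, but that is an inference.

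**The effect size is assumed.** This also stands. At d = 0.1 even a fixed order barely raises the error rate, and the 80% figure pairs a large effect with the most extreme split. Completed surveys may also fall below 34, because Section 3.3.1 removes patients whose lesion is not visible or who miss CT/MRI, and Section 10.0 lets subjects skip questions.

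**The data forms cannot be seen.** Section 7.0 keeps survey and data-collection materials out of the protocol, so a field for exam order may exist. A direct preference question asked after both exams would also not follow the simple shift model. Both are fair. Even so, Section 8.3 makes no use of order, recorded or not.

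**Forcing the order could disturb care.** Section 7.2.2 says that trial participation must not affect follow-up timing. CEUS first would add time ahead of a booked scan, given at least 15 minutes of monitoring (Section 9.2). A strict 17/17 assignment must therefore yield to the clinical appointment. The order-averaged estimate does not need exact balance, so the remedy survives in softer form.

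**It is the third objective of an exploratory pilot.** That is so in Sections 1.1 and 8.3, although Section 1.2 lists the survey among the primary endpoints and Section 8.3 plans a formal test. It limits the weight of the point but does not remove it.

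**Conclusion.** The point holds in a limited form. The protocol leaves exam order unspecified and unbalanced, makes no provision for recording it, and ignores it in the analysis. An order effect on the anxiety and comfort ratings can therefore be neither ruled out nor adjusted for. Attribution to modality would be complete if everyone follows one sequence, partial if the order is unbalanced, and about nil on average if the order is balanced and unrelated to preference.

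A reader might infer more: that the order is set by convenience, and that the comparison is therefore confounded outright. The text does not support this. The remarks on convenience ("allowing patient convenience and privacy to simply move between rooms for both exams" in Section 7.2.2 and "due to convenience and privacy of the patient" in Section 15.1) concern having both exams in one place. So does "This visit will be performed at either the main hospital or our East Campus, depending on availability and patient needs", which decides the campus. None of them speaks to sequence.

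The size of any distortion is unknown. The rates above rest on an assumed constant order effect, SD 1, no true modality difference and 34 complete pairs. The diagnostic accuracy comparison is not touched.

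**What to change.** **Section 7.2.2.** Alternate the order of CEUS and CT/MRI, or take it from a simple list, where scheduling allows. Do not move the clinically ordered CT/MRI appointment. Record in REDCap the order actually followed, including when it departs from the assigned one.

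**Section 8.3.** Report ratings by order. Estimate the modality difference as the average of the two order-specific differences, with a matching order-stratified test. If nearly all patients turn out to follow one order, state that modality and order cannot be separated.

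**Cost.** One data field, a few lines of text and some scheduling effort. Some visits will not be able to follow the assigned order, and precision is somewhat lower if the order stays unbalanced (about 18% wider standard error at 26/8). Recording the order is the least that should be done, since it is nearly free and cannot reliably be recovered later.
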